After blood collection, participants will be given breakfast (orange juice, toast and jam, tea or coffee). Following consumption of breakfast, participant's diet will be assessed using the widely used EPIC Food Frequency Questionnaire, their quality of life will be assessed using EQ5D5L and their physical activity will be assessed using PASE. Participants will then be randomised to one of four groups (vitamin D (calcifediol, 10 µg/day), probiotic (*Lactobacillus plantarum* TIFN101 (5 x 10^9 cfu/day)), vitamin D + probiotic, or placebo) and will receive 3 months supply along with a diary to record that they have taken their supplement each day. Blinding, randomisation, and supplement packaging will be completed by individuals independent of the researchers involved in the study. Participants will be randomised stratified by sex to ensure equal numbers of males and females in each treatment group.

Participants will also take away materials for collection of faecal and urine samples. They will be provided with a pack and instructions for collecting a faecal sample and 3 urine samples at home within one week of V1. Two urine samples will be collected on weekdays (one per day) and one urine sample will be collected at a weekend or first thing on a Monday morning. Participants will be asked to complete a 24 hr food diary using the online tool 'intake 24' or by completing a

paper diary 24 hr prior to collecting each urine sample. Participants will be asked to keep the urine samples in their home fridge until all 3 samples have been collected. Participants will be asked to collect a faecal sample within 24 hours of the last urine collection. Participants will be asked to either return their samples to the Clinical Research Facility in person or to contact the researcher once samples are available who will travel to their home to collect the samples or will arrange for them to be collected by courier.

At the end of V1 participants will be provided with their supplements and instructed to start taking these once they have produced their faecal sample and three urine samples. Participants will receive instructions on taking their supplements and will record this daily use in a paper diary.

Participants will be contacted every 4 weeks by the researcher (at week 4 and week 8) and will be requested to bring unused supplements to their end of study clinic visit (visit 2; week 12). These will be used to assess compliance.

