#### 5. Sample size and statistical analysis

The primary outcomes of the study are serum 25-hydroxyvitamin D3 concentration, colonisation with the probiotic organism (as detected in faeces), and serum CRP concentration. The study sample size has been calculated based upon blood 25-hydroxyvitamin D3 concentration. Assuming a study entry concentration of 45 nmol/l and an increase to 70 nmol/l after receiving 10 µg/day calcifediol for 3 months (both with a standard deviation of 25 nmol/l), a sample size of 72 (n = 36 per group i.e. + or – vitamin D) will give 95% power to detect the difference in concentrations as significant at  $p < 0.01$ . To allow for a drop-out rate of 30% a total of 104 participants will be enrolled. This sample size will be sufficient to detect colonisation with the probiotic, as such colonisation (with other organisms) has been shown with smaller sample sizes. Using our data for serum CRP concentrations in older people resident in care homes (mean 6.3 ± 2.2 mg/dl) we estimate that a sample size of study completers of 36 per group will give 70% power to detect a 20% reduction as significant.

Changes between V1 and V2 in all outcomes will be compared between groups by ANOVA for 2 x 2 factorial design; subsequent pairwise comparisons between groups will be performed. Statistical analysis will be conducted using the current version of SPSS.

Study materials (i.e. the supplements) will be provided prepackaged by DSM. DSM will allocate a study ID to each participant's package of supplements in order that both participants and researchers are blind to allocation. DSM will provide to the researchers a sealed envelope (one per participant) containing the treatment allocation for each participant. These envelopes will be kept in a locked filing cabinet and will be accessed a) if there is a SAE and b) once the database is complete and locked and prior to statistical analysis being performed.

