## **6. Adverse events**

### **6.1 What is an adverse event?**

An adverse event (AE) is defined as any untoward medical occurrence in a patient or clinical study subject administered an investigational product and which does not necessarily have a causal relationship with this treatment. An AE can therefore be any unfavourable and unintended sign (including an abnormal laboratory finding), symptom, or disease temporally associated with the use of an investigational product, whether or not related to the investigational product.

An adverse reaction is defined as all untoward and unintended responses to an investigational product related to any dose administered, i.e. where a causal relationship between the investigational product and an adverse event is at least a reasonable possibility.

An unexpected adverse reaction is an adverse reaction, the nature or severity of which is not consistent with the information about the investigational product or intervention in question set out in the Summary of Product Characteristics or Investigator's Brochure.

An adverse event, adverse reaction, or unexpected adverse reaction, is defined as serious if it:

- a) results in death;
- b) is life-threatening;  
Life threatening in the definition of a serious adverse event (SAE)/serious adverse reaction (SAR) refers to an event in which the subject was at risk of death at the time of the event; it does not refer to an event that hypothetically might have caused death if it were more severe.
- c) requires hospitalisation or prolongation of existing hospitalisation;  
In general, hospitalisation signifies that the participant has been detained (usually involving an overnight stay) at the hospital or emergency ward for observation and/or treatment which would not have been appropriate at the investigator site. When in doubt as to whether hospitalisation occurred or was necessary, the adverse event should be considered as serious. Hospitalisation for elective surgery or routine clinical procedures, which are not the result of an AE, need not be considered AE and should be recorded on a Clinical Assessment form and added to the study file. If something untoward is reported during the procedure, this must be reported as an AE and either 'serious' or 'non-serious' attributed according to the usual criteria.
- d) results in persistent or significant disability or incapacity;
- e) consists of a congenital anomaly or birth defect.

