## **6.3 Causality**

The relationship between the investigational product/procedure and the occurrence of each AE will be assessed and categorised as below by the investigator. The investigator will use clinical judgement to determine the relationship. Alternative causes, such as natural history of the underlying diseases, concomitant therapy, other risk factors etc. will be considered. The Investigator will also consult the IB or other product information.

- Not related: Temporal relationship of the onset of the event, relative to administration of the product, is not reasonable or another cause can by itself explain the occurrence of the event.
- Unlikely: Temporal relationship of the onset of the event, relative to administration of the product, is likely to have another cause which can by itself explain the occurrence of the event.
- Possibly related: Temporal relationship of the onset of the event, relative to administration of the product, is reasonable but the event could have been due to another, equally likely cause.
- Probably related: Temporal relationship of the onset of the event, relative to administration of the product, is reasonable and the event is more likely explained by the product than any other cause.
- Definitely related: Temporal relationship of the onset of the event, relative to administration of the product, is reasonable and there is no other cause to explain the event, or a re-challenge (if feasible) is positive.
- Where an event is assessed as possibly related, probably related, definitely related the event is an adverse reaction.

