## **6.4 Expectedness**

Adverse reactions must be considered as unexpected if they add significant information on the specificity or severity of an expected adverse reaction. The expectedness of an adverse reaction shall be determined according to the reference documents.

- Expected: Reaction previously identified and described in protocol and/or reference documents.
- Unexpected: Reaction not previously described in the protocol or reference documents.

All AEs occurring during the period from screening visit to the trial completion will be registered and reported if applicable.

For all adverse event/reactions the investigator will make an assessment of intensity, causality, expectedness and seriousness.

The PI will keep the Sponsor and the REC informed of any significant findings.

At the end of the study all adverse events recorded during the study will be subject to statistical analysis and analysis and subsequent conclusions will be included in the final study report. All AEs experienced by study subjects will be registered. After trial completion these study subjects will be unblinded.

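### Any SAE, related or not, opens an allocation envelope held by the researchers meant to be blind, and no blinded causality judgement is required first

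*Protocol*

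**What the plan says.** Section 3 (Visit 1) separates the researchers from the allocation: "Blinding, randomisation, and supplement packaging will be completed by individuals independent of the researchers involved in the study". Section 5 repeats the aim, with packages given study IDs "in order that both participants and researchers are blind to allocation". The same paragraph then passes the code to those researchers: "DSM will provide to the researchers a sealed envelope (one per participant) containing the treatment allocation for each participant". The envelopes stay in a locked cabinet and "will be accessed a) if there is a SAE and b) once the database is complete and locked". The second occasion falls before the statistical analysis.

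Section 6.1 defines an adverse event as an occurrence "which does not necessarily have a causal relationship with this treatment". On hospitalisation it adds that, in doubtful cases, "the adverse event should be considered as serious". It exempts admissions for elective surgery or routine procedures that do not result from an adverse event. Section 6.3 says the relationship of each event to the product "will be assessed and categorised as below by the investigator". Section 6.4 states that all adverse events will be registered and analysed statistically, and, of the participants who had them, "After trial completion these study subjects will be unblinded".

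**The concern.** The rule for breaking the code is tied to the wrong property of the event. Seriousness describes the outcome of an event. It does not show that anyone needs to know the allocation. A clearly unrelated serious event therefore breaks the blind for that participant and nothing is gained.

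What is mainly at stake is the safety comparison. Causality is a five-level clinical judgement, and the top three levels turn an event into an adverse reaction. An assessor who knows that the participant took placebo, or active product, can be moved by that knowledge. The judgement then enters the analysis of adverse events. A lesser stake is the Visit 2 assessment of a participant who had an SAE earlier and stayed in the trial, where an assessor who knows the allocation could affect a measure such as grip strength.

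Sections 5 and 6.4 also give different times for unblinding a participant who has had an SAE, and neither refers to the other.

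**Working it through.** No figure in the protocol is at issue, so the check is mainly a comparison of provisions.

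**1. Trigger.** Section 5 uses directive wording and sets one condition, that an SAE has occurred. By section 6.1 an adverse event, and so an SAE, may be unrelated to the product. The trigger therefore includes unrelated events. Section 6.1 also defines narrower classes (SSAR and SUSAR), and section 6.5 reports SUSARs and SAEs by different routes. Section 5 uses none of these distinctions, and section 6.5 gives no unblinding step for either class.

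**2. Custody.** The researchers are to be blind and also hold the envelopes. The protocol names no person to open one, asks for no log, and does not separate the opener from those who assess outcomes.

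**3. Order.** Section 6.3 assigns causality to the investigator. No section says whether that judgement comes before or after opening. A blinded judgement is possible under the text but is not secured by it.

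**4. Timing.** Every SAE is an adverse event. Under section 5 the participant's allocation is opened at the event. Under section 6.4 participants with adverse events are unblinded after trial completion. Section 5 may be meant as an exception to section 6.4, but neither says so.

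**5. Reach.** There is one envelope per participant, so one opening exposes one allocation, to whoever opens it. Visit 2 measures are affected only if the SAE occurs before Visit 2 and the participant continues. Adverse events are collected from the screening visit to trial completion, so not every SAE meets that condition.

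**6. Scale.** Inputs: 104 participants enrolled (section 5) and an SAE rate r per participant, which the protocol does not give and which is assumed here.

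- Expected envelopes opened = 104 × r
- Chance of at least one = 1 − (1 − r)^104, taking participants as independent

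| Assumed r | Envelopes opened | Chance of at least one |
|---|---|---|
| 1% | 104 × 0.01 = 1.04 | 1 − 0.99^104 = 65% |
| 3% | 104 × 0.03 = 3.12 | 1 − 0.97^104 = 96% |
| 5% | 104 × 0.05 = 5.2 | 1 − 0.95^104 = 99.5% |
| 10% | 104 × 0.10 = 10.4 | over 99.9% |

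Section 5 plans for 72 completers, 36 with and 36 without vitamin D. One participant is 1/36 = 2.8% of such a group, or 1/18 = 5.6% of one of the four cells (72/4 = 18).

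**The case against.** The strongest reply is that the protocol prescribes no unblinded assessment. It does not order the opening against the causality judgement, and it does not say that the investigator opens the envelope. A reader might infer that every SAE causality call is made with the allocation known, or that the whole research team is unblinded. The text supports neither: the first needs an order that is not stated, and the second overlooks that the envelopes are individual.

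Nor does section 6.4 flatly contradict section 5. It does not say that unblinding happens only after completion, so it can be read as the general rule with section 5 as the SAE exception. That is fair. What remains is an exception that the protocol never declares.

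The effect on outcomes is also easy to overstate. The three primary outcomes (serum 25-hydroxyvitamin D3, *L. plantarum* in faeces, serum CRP) are laboratory measures. The respiratory questionnaire is completed between visits. Nothing says the participant is told the allocation, so bias in the self-reported EQ5D5L and PASE cannot be assumed. Grip strength is one of many secondary outcomes, and the protocol does not say who takes the reading. Not every admission is an SAE, given the exemption for elective and routine ones.

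These points limit the size of the problem. They do not touch the unconditional trigger, the custody, or the lack of any safeguard for a blinded judgement.

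**Conclusion.** The point holds in a limited form. As written, the rule breaks the blind for any SAE without regard to relatedness or need, through envelopes held by people who are meant to be blind, and nothing requires causality to be recorded first. This is a stated rule with an avoidable cost, not detail left for an analysis plan.

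The number affected is small: about 1 to 10 of 104 at assumed SAE rates of 1% to 10%, and fewer for Visit 2 measures. The main exposure is SAE causality and adverse event recording. Researcher-measured secondary outcomes such as grip strength come second, on the assumption that whoever knows the allocation also takes the measurement. The documents give no ground for doubting the primary comparisons on this account. The change is worth making because it is cheap and protects the safety comparison in a trial described as double-blind.

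**What to change.** - Reconcile sections 5 and 6.4 so that an SAE does not by itself open the envelope, state the condition for opening, and cross-refer the two sections. What that condition should be is for the sponsor and the clinical team to decide.
- Require the blinded causality assessment of section 6.3 to be recorded before the envelope is opened, where urgency allows.
- Have the envelopes held and opened by someone who assesses neither causality nor Visit 2 outcomes, with the date and reason logged.

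The cost is protocol wording, a change of custody and a log. The holder must be reachable, so that urgent access is kept.

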## **6. Adverse events**

### **6.1 What is an adverse event?**

An adverse event (AE) is defined as any untoward medical occurrence in a patient or clinical study subject administered an investigational product and which does not necessarily have a causal relationship with this treatment. An AE can therefore be any unfavourable and unintended sign (including an abnormal laboratory finding), symptom, or disease temporally associated with the use of an investigational product, whether or not related to the investigational product.

An adverse reaction is defined as all untoward and unintended responses to an investigational product related to any dose administered, i.e. where a causal relationship between the investigational product and an adverse event is at least a reasonable possibility.

An unexpected adverse reaction is an adverse reaction, the nature or severity of which is not consistent with the information about the investigational product or intervention in question set out in the Summary of Product Characteristics or Investigator's Brochure.

An adverse event, adverse reaction, or unexpected adverse reaction, is defined as serious if it:

- a) results in death;
- b) is life-threatening;  
Life threatening in the definition of a serious adverse event (SAE)/serious adverse reaction (SAR) refers to an event in which the subject was at risk of death at the time of the event; it does not refer to an event that hypothetically might have caused death if it were more severe.
- c) requires hospitalisation or prolongation of existing hospitalisation;  
In general, hospitalisation signifies that the participant has been detained (usually involving an overnight stay) at the hospital or emergency ward for observation and/or treatment which would not have been appropriate at the investigator site. When in doubt as to whether hospitalisation occurred or was necessary, the adverse event should be considered as serious. Hospitalisation for elective surgery or routine clinical procedures, which are not the result of an AE, need not be considered AE and should be recorded on a Clinical Assessment form and added to the study file. If something untoward is reported during the procedure, this must be reported as an AE and either 'serious' or 'non-serious' attributed according to the usual criteria.
- d) results in persistent or significant disability or incapacity;
- e) consists of a congenital anomaly or birth defect.

Medical judgement should be exercised in deciding whether an SAE/SAR is serious in other situations. Important SAE/SARs that are not immediately life-threatening or do not result in death or prolonged hospitalisation but may jeopardise the subject or may require intervention to prevent one or the other outcomes listed in the definition above, should also be considered serious.

A suspected serious adverse reaction (SSAR), is any serious adverse reaction that is suspected (possibly or probably) to be related to the investigational product.

A suspected unexpected serious adverse reaction (SUSAR) is an SSAR which is also “unexpected”, meaning that its nature and severity are not consistent with the information about the investigational product in question set out in the IB.

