#### **6.5 Expedited reporting of serious adverse events**

All patient safety related incidents will be reported according to University Hospital Southampton NHS Foundation Trust (UHS) Incident Reporting and Management Policy. In addition to the Trust Incident reporting, SAEs are expedited to the people and departments identified below. The PI (or delegated person) will make an initial report, orally or in writing. The initial report will include as much information as is available at the time.

The PI (or delegated person) will report the following:

SUSAR

Immediately report to:

- the PI
- the sponsor
- UHS R&D department
- UHS patient safety team (using Trust incident Reporting form)
- the University of Southampton

UHS will be responsible to further expedite the Reporting of SUSAR to the REC that gave approval as soon as possible but within 7 days. The investigator (or delegated person) will make an initial report, orally or in writing. The initial report will include as much information as is available at the time. Oral reports will be followed up in writing within a further 24 hours of the initial report.

After the initial report the investigator will actively follow up the subject. The Investigator (or delegated person) will provide information missing from the initial report within five working days of the initial report.

Written reports will be made by completing an SAE/SUSAR reporting form provided by University Hospital Southampton R&D.

UHS incident report template available from UHS Staffnet or departmental log books

SAE

Within 24 hours report to:

- the PI
- the Sponsor
- UHS R&D Department
- the University of Southampton

As above; but no expedited reporting to the REC.

Urgent Safety Measures/ Temporary Halt of the Trial

Implement and report immediately as a substantial amendment to:

- the PI
- the Sponsor

The PI

must inform as soon as possible but within 3 days:

- the REC that granted approval
- the University of Southampton

The Sponsor and the PI must be notified of any urgent safety measures/temporary halt of a trial that have had to be taken that are not part of the protocol.

The report must include the reasons for the urgent safety measure and the plan for further action.

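### Read literally, the SUSAR definition in section 6.1 is narrower than the protocol's own rules on unexpectedness and causality, so some unexpected serious reactions could miss the 7-day ethics committee report

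*Protocol*

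**What the plan says.** The protocol describes unexpectedness in three places.

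- Section 6.1, general definition: an unexpected adverse reaction is one "the nature or severity of which is not consistent with the information about the investigational product or intervention in question". The reference is the Summary of Product Characteristics or the Investigator's Brochure.
- Section 6.1, SUSAR definition: a suspected serious adverse reaction (SSAR) that is also unexpected, "meaning that its nature and severity are not consistent with the information". Only the Investigator's Brochure is named.
- Section 6.4: "Adverse reactions must be considered as unexpected if they add significant information on the specificity or severity of an expected adverse reaction". The same section classes as unexpected any reaction not already described in the protocol or the reference documents.

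It describes relatedness in two places.

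- Section 6.1 defines an SSAR as a serious adverse reaction that is "suspected (possibly or probably) to be related to the investigational product".
- Section 6.3 has five causality categories and says that where an event is assessed as "possibly related, probably related, definitely related the event is an adverse reaction".

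Section 6.5 attaches duties to the labels. A SUSAR is reported immediately to the PI, the sponsor, the hospital's R&D department, its patient safety team and the University. The hospital must then "expedite the Reporting of SUSAR to the REC that gave approval as soon as possible but within 7 days". Any other serious adverse event is reported within 24 hours to the same parties except the patient safety team: "As above; but no expedited reporting to the REC".

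**The concern.** The SUSAR definition does not simply refer back to the general definition of an unexpected reaction. It restates the meaning, joins the two criteria with *and*, and names a narrower reference source. Taken at face value, it is a second and stricter test, attached to the one label that triggers expedited reporting.

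The SSAR bracket works in the same direction. A SUSAR must first be an SSAR, so if the bracket is read as a complete list, a reaction assessed as definitely related cannot become a SUSAR. That would exclude the reactions with the strongest causal evidence.

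At stake is how promptly the REC hears of an unexpected serious reaction. Both discrepancies lean towards under-reporting.

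**Working it through.** There is no figure to reproduce. The check is to apply each wording to every type of serious adverse reaction and see where the answers differ.

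**Step 1: unexpectedness.** Nature and severity can each be consistent or not consistent with the reference information, which gives 2 × 2 = 4 combinations.

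| Nature | Severity | Unexpected under 6.1 general definition and 6.4? | Unexpected under 6.1 SUSAR wording, read literally? |
|---|---|---|---|
| consistent | consistent | no | no |
| not consistent | consistent | yes | no |
| consistent | not consistent | yes | no |
| not consistent | not consistent | yes | yes |

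The rules disagree in 2 of the 4 combinations. The severity-only row is the clearest: section 6.4 addresses it directly, since a listed reaction in a more severe form adds information on severity. The nature-only row is less clear in practice. An unlisted reaction has no listed severity to compare with, so some assessors would treat both criteria as not met and still reach SUSAR.

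**Step 2: causality.** Section 6.3 counts three categories as adverse reactions: possibly, probably and definitely related. The SSAR bracket names the first two. The omission changes the reporting route only if the reaction is also unexpected. A definitely related reaction that is expected is not a SUSAR under any of the wordings and has no 7-day report to lose.

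**Step 3: both together.** There are 3 causality categories × 4 combinations = 12 types of serious adverse reaction.

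- SUSAR if the general definition, section 6.4 and section 6.3 govern: 3 causality categories × 3 unexpected combinations = 9 types.
- SUSAR on the literal SSAR and SUSAR wording: 2 causality categories × 1 combination = 2 types.
- Types on which the wordings differ: 9 − 2 = 7. Of these, 4 arise from *and* alone (possibly or probably related, one departure only), 1 from the bracket alone (definitely related, both departures), and 2 from either (definitely related, one departure only).

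These are types of event, not frequencies. The protocol gives no expected rate of serious reactions, so no event count can be derived.

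**Step 4: what changes for an affected event.** Under section 6.5 it would move from immediate reporting, a patient-safety-team notice and a REC report within 7 days to reporting within 24 hours with no expedited REC report. The PI, sponsor, R&D department and University are informed on both routes.

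**The case against.** Four points can be made for the protocol.

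1. *The protocol already has a sound rule.* The general definition in section 6.1 uses *or*. Section 6.4 is the dedicated section on expectedness, is worded as mandatory, and covers both gap cases: the listed reaction that is more severe and the reaction not described before. It also requires an expectedness assessment for every event. This stands as a limit on the consequence. An investigator who works from section 6.4 would class these reactions as unexpected, so a report *could* be missed. A reader might infer that it *would* be missed, and the protocol does not support that. The contradiction itself remains, because nothing says which definition prevails.

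2. *The conjunction can be read loosely.* Saying that nature and severity are not consistent may mean only that they are not both consistent, which agrees with the other two places. The reading is possible, but a safety definition should not depend on the reader choosing it.

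3. *The bracket may only explain how much suspicion is enough.* Section 6.1 sets the threshold for an adverse reaction at a reasonable possibility or more, and section 6.3 expressly includes the definitely related class. That is probably what was meant. A reader might also infer that every definitely related serious reaction drops from a 7-day report to none. That is wrong: the expected ones never had such a report (step 2).

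4. *Other safeguards remain.* The 24-hour reports are unaffected, section 6.5 puts all patient safety incidents under the hospital's incident policy, and section 6.4 has the PI keep the sponsor and the REC informed of significant findings. This stands and keeps the matter minor. None of these sets the 7-day limit for the REC.

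**Conclusion.** Wrong as written: an internal contradiction in an operative safety-reporting rule, of minor severity. The SUSAR wording, read literally, conflicts with the general definition in section 6.1 and with section 6.4, and the SSAR bracket leaves out a class that section 6.3 includes.

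The exposure covers a suspected serious reaction that is unexpected in nature only or in severity only, and one that is unexpected and assessed as definitely related. Such an event could miss the 7-day REC report and the patient-safety-team notice listed for SUSARs. This rests on staff applying the SSAR and SUSAR wording literally rather than sections 6.3 and 6.4.

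With 104 participants to be enrolled and 3 months of supplementation, few such events are likely, although the protocol gives no rate from which to estimate the number. The sample size, outcomes and planned analysis are unaffected.

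**What to change.** Reconcile the SSAR and SUSAR definitions in section 6.1 with the protocol's own text:

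- In the SUSAR definition, write *nature or severity*, as in the general definition, or refer back to that definition and to section 6.4 without restating the meaning.
- In the SSAR definition, write *(possibly, probably or definitely)*, to match section 6.3.
- Name the same reference documents throughout. At present the general definition names the Summary of Product Characteristics or the Investigator's Brochure, the SUSAR definition only the Investigator's Brochure, and section 6.4 the protocol and/or reference documents.

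The cost is a few words in the protocol and at most a few more expedited reports. No visit, measurement or analysis changes.
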